### 14.5.2 Methods for Assessing, Recording and Analyzing Safety Parameter(s)

All laboratory results have to be evaluated in the eCRF according to the following pattern:

- a) outside reference range but not clinically relevant (e.g. due to already known conditions, due to sampling conditions, only marginal deviation, due to underlying diseases in the study population)
- b) outside reference range and clinically relevant.

Laboratory values which are outside the reference range and assessed as clinically relevant have to be controlled and documented as adverse events if they occur for the first time after administration of investigational medicinal product BT524.

If abnormal laboratory values are signs of an adverse event (e.g. an infection) that has already been reported during the present study, this has to be stated but the respective abnormal laboratory value does not constitute a separate adverse event.

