11.1 Adverse events

All assessments will be done for all patients, part I and part II separately.

Adverse events (AE) will be coded using the MedDRA® dictionary. The current version will be used at time of database lock and presented by primary System Organ Class (SOC) and Preferred Term.

The analysis will focus on the treatment-emergent AEs (TEAEs). When an AE occurs after written consent has been obtained but before the first dose of study drug, the AE will be considered a non-treatment emergent AE. An AE that occurs (or worsened) on or after the time the patient receives his/her first dose of study drug (until his/her last study visit) will be considered a treatment emergent AE (TEAE). See also CSP section 14.6.2 for definition of non-treatment adverse events.

Please note the definition of study periods and adverse event reporting periods in section 5.5 above. Please also note that analyses for TEAE will be based on the safety population (SAF). Overview tables including non-TEAEs will be based on the APE to also include patients not treated in the study.

For the analysis of TEAEs only those TEAEs are taken into consideration which are reported from first treatment to the safety visit after treatment (independent of the planned duration between treatment start and Day 49 safety visit). For part I this is the duration between PK treatment and the Day 49 PK safety visit or earlier (if a bleeding event happened before Day 49 PK safety visit), and for part II this is for each bleeding event the duration between treatment of the bleeding event and Day 49 safety visit or earlier (if another bleeding event happened before Day 49 safety visit).

All other TEAEs reported out of these time frames will be counted and listed. Exception is the analysis of related serious adverse events (related SAEs) which are included in the analysis irrespective of the onset time after first administration of IMP:

If 'Day 49 safety visit' is not done, the period for inclusion of TEAEs in the analysis is from baseline (treatment start) to 49 days post-baseline.

The total number and percentage of patients reporting at least one AE and the absolute count of AEs will be tabulated for each age group and overall. This initial summary will be based on the APE set and provide a breakdown of the following:

- Any AE
- Any non-severe AE
- Any TEAE
- Any non-serious TEAE
- Any non-severe TEAE
- Any treatment-related TEAE
- Any severe AE

- Any severe TEAE

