- Any severe treatment-related TEAE
- Any SAE
- Any serious TEAE
- Any serious treatment-related TEAE
- Any AE leading to discontinuation from study
- Any TEAE leading to discontinuation from study
- Any treatment-related TEAE leading to discontinuation from study
- Any AE with outcome of death
- Any death
- Any pregnancy

In the SAF number and frequencies (i.e. percentages) of patients with TEAEs will be given by System Organ Class (SOC) and by Preferred term within each SOC (total, for each age group) together with the number of events for the following:

1. All TEAEs
2. Serious TEAEs
3. All TEAEs considered related (see details below)
4. Serious TEAEs considered related (see details below)
5. All TEAEs by maximum severity ('mild', 'moderate', 'severe')
6. TEAEs leading to death
7. TEAEs leading to study discontinuation
8. The TEAEs occurring under infusion and within 24 hours after the start of IMP infusion (Infusion related reaction (IRR))
9. Related TEAEs occurring within 24 hours after start of infusion
10. Adverse events of special interest (AESI):
 - Hypersensitivity/ Anaphylactic reactions/anaphylactic shock: Hypersensitivity (SMQ, restricted to narrow search), Anaphylactic reaction (SMQ, restricted to narrow search), "Anaphylactic shock conditions" (SMQ, restricted to narrow search)
 - Thrombogenicity: SMQ Embolic and thrombotic events (restricted to narrow search)
 - Transmission of infective agents: Preferred Term "Transmission of infectious agent via product" and "Suspected transmission of an infectious agent via product (Preferred Term)
 - Fibrinogen inhibitory antibodies: SOC"Investigations"
11. Related AESI:

- Hypersensitivity/ Anaphylactic reactions/anaphylactic shock: Hypersensitivity (SMQ, restricted to narrow search), Anaphylactic reaction (SMQ, restricted to narrow search), "Anaphylactic shock conditions" (SMQ, restricted to narrow search)
- Thrombogenicity: SMQ Embolic and thrombotic events (restricted to narrow search)
- Transmission of infective agents: Preferred Term "Transmission of infectious agent via product" and "Suspected transmission of an infectious agent via product (Preferred Term)
- Fibrinogen inhibitory antibodies: SOC"Investigations"

Additionally, number and frequencies of patients with TEAEs will be presented by decreasing frequency for all TEAEs, serious TEAEs and TEAEs considered related.

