11.6 Fibrinogen inhibitory antibodies

Fibrinogen inhibitory antibodies are locally measured from sampling at screening, pre-dose (if applicable) and at the safety visit and will be categorized as positive, negative, or missing/not done.

Number of patients and percentages in each category will be summarized for part I (PK) and part II for SAF and on event level from part II for FBE. A listing with all patients fibrinogen inhibitory antibodies data will also be presented.

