Table	14.3.2.13.3	Treatment-Emergent Adverse Events with Transmission of Infectious Agents by Age Group: Frequencies and Percentages of Patients by SOC and Preferred Term – SAF I
Table	14.3.2.13.4	Treatment-Emergent Adverse Events with Transmission of Infectious Agents by Age Group: Frequencies and Percentages of Patients by SOC and Preferred Term – SAF II
Table	14.3.2.14.1	Treatment-Emergent Adverse Events with Fibrinogen Inhibitory Antibodies: Frequencies and Percentages of Patients by SOC and Preferred Term – SAF I and II
Table	14.3.2.14.2	Treatment-Emergent Adverse Events with Fibrinogen Inhibitory Antibodies: Overall by Age Group: Frequencies and Percentages of Patients by SOC and Preferred Term – SAF I and II
Table	14.3.2.14.3	Treatment-Emergent Adverse Events with Fibrinogen Inhibitory Antibodies by Age Group: Frequencies and Percentages of Patients by SOC and Preferred Term – SAF I
Table	14.3.2.14.4	Treatment-Emergent Adverse Events with Fibrinogen Inhibitory Antibodies by Age Group: Frequencies and Percentages of Patients by SOC and Preferred Term – SAF II
Table	14.3.2.15.1	Treatment-Emergent Related Adverse Events with Hypersensitivity/Anaphylactic reaction/Anaphylactic Shock: Frequencies and Percentages of Patients by SOC and Preferred Term – SAF I and II

Table	14.3.2.15.2	Treatment-Emergent Related Adverse Events with Hypersensitivity/Anaphylactic reaction/Anaphylactic Shock: Overall by Age Group: Frequencies and Percentages of Patients by SOC and Preferred Term – SAF I and II
Table	14.3.2.15.3	Treatment-Emergent Related Adverse Events with Hypersensitivity/Anaphylactic reaction/Anaphylactic Shock by Age Group: Frequencies and Percentages of Patients by SOC and Preferred Term – SAF I
Table	14.3.2.15.4	Treatment-Emergent Related Adverse Events with Hypersensitivity/Anaphylactic reaction/Anaphylactic Shock by Age Group: Frequencies and Percentages of Patients by SOC and Preferred Term – SAF II
Table	14.3.2.16.1	Treatment-Emergent Related Adverse Events with Thrombogenicity: Frequencies and Percentages of Patients by SOC and Preferred Term – SAF I and II
Table	14.3.2.16.2	Treatment-Emergent Related Adverse Events with Thrombogenicity: Overall by Age Group: Frequencies and Percentages of Patients by SOC and Preferred Term – SAF I and II
Table	14.3.2.16.3	Treatment-Emergent Related Adverse Events with Thrombogenicity by Age Group: Frequencies and Percentages of Patients by SOC and Preferred Term – SAF I

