Table	14.3.2.16.4	Treatment-Emergent Related Adverse Events with Thrombogenicity by Age Group: Frequencies and Percentages of Patients by SOC and Preferred Term – SAF II
Table	14.3.2.17.1	Treatment-Emergent Related Adverse Events with Transmission of Infectious Agents: Frequencies and Percentages of Patients by SOC and Preferred Term – SAF I and II
Table	14.3.2.17.2	Treatment-Emergent Related Adverse Events with Transmission of Infectious Agents: Overall by Age Group: Frequencies and Percentages of Patients by SOC and Preferred Term – SAF I and II
Table	14.3.2.17.3	Treatment-Emergent Related Adverse Events with Transmission of Infectious Agents by Age Group: Frequencies and Percentages of Patients by SOC and Preferred Term – SAF I
Table	14.3.2.17.4	Treatment-Emergent Related Adverse Events with Transmission of Infectious Agents by Age Group: Frequencies and Percentages of Patients by SOC and Preferred Term – SAF II
Table	14.3.2.18.1	Treatment-Emergent Related Adverse Events with Fibrinogen Inhibitory Antibodies: Frequencies and Percentages of Patients by SOC and Preferred Term – SAF I and II
Table	14.3.2.18.2	Treatment-Emergent Related Adverse Events with Fibrinogen Inhibitory Antibodies: Overall by Age Group: Frequencies and Percentages of Patients by SOC and Preferred Term – SAF I and II
Table	14.3.2.18.3	Treatment-Emergent Related Adverse Events with Fibrinogen Inhibitory Antibodies by Age Group: Frequencies and Percentages of Patients by SOC and Preferred Term – SAF I
Table	14.3.2.18.4	Treatment-Emergent Related Adverse Events with Fibrinogen Inhibitory Antibodies by Age Group: Frequencies and Percentages of Patients by SOC and Preferred Term – SAF II
Listing	16.9.1	All Adverse Events – APE I and II

Listing	16.9.2	Serious Adverse Events – APE I and II
Listing	16.9.3	Adverse Events Leading to Death – APE I and II
Listing	16.9.4	Adverse Events Leading to Study Discontinuation – APE I and II
Laboratory data		
Table	14.3.3.1.1	Haematology Laboratory Data: Descriptive Statistics of RBC, WBC, Platelet, Hemoglobin, Hematocrit by Time Point – SAF I
Table	14.3.3.1.2	Haematology Laboratory Data: Frequencies and Percentages of Clinically Significant RBC, WBC, Platelet, Hemoglobin, Hematocrit by Time Point – SAF I
Table	14.3.3.1.3	Haematology Laboratory Data on Event Level: Descriptive Statistics of RBC, WBC, Platelet, Hemoglobin, Hematocrit by Indication and Time Point – FBE

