Listing	16.16.2	Physical Examination - Investigator Clinically Significant Findings – SAF I
Listing	16.16.3	Physical Examination – FBE
Listing	16.16.4	Physical Examination - Investigator Clinically Significant Findings – FBE
Fibrinogen Inhibitory Antibodies		
Table	14.3.4.5.1	Fibrinogen Inhibitory Antibodies Data: Frequencies and Percentages of Patients by Time Point – SAF I
Table	14.3.4.5.2	Fibrinogen Inhibitory Antibodies Data: Frequencies and Percentages of Patients by Time Point – SAF II
Table	14.3.4.5.3	Fibrinogen Inhibitory Antibodies Data on Event Level: Frequencies and Percentages of Patients by Time Point – FBE
Listing	16.17.1	Fibrinogen Inhibitor Antibodies – SAF I
Listing	16.17.2	Fibrinogen Inhibitor Antibodies – FBE
Markers of coagulation activation		
Table	14.3.4.6.1	Coagulation Activation Data: Descriptive Statistics of PT, PT (INR), aPTT, TAT, F1+2, D-dimer by Time Point – SAF I
Table	14.3.4.6.2	Coagulation Activation Data: Frequencies and Percentages of clinically significant of PT, PT (INR), aPTT, TAT, F1+2, D-dimer by Time Point without Hospitalization – SAF I
Table	14.3.4.6.3	Coagulation Activation Data on Event Level: Descriptive Statistics of PT, PT (INR), aPTT, TAT, F1+2, D-dimer by Indication and Time Point – FBE
Table	14.3.4.6.4	Coagulation Activation Data on Event Level by Age Group: Descriptive Statistics of PT, PT (INR), aPTT, TAT, F1+2, D-dimer by Time Point – FBE
Table	14.3.4.6.5	Coagulation Activation Data on Event Level by Hospitalization: Descriptive Statistics of PT, PT (INR), aPTT, TAT, F1+2, D-dimer by Time Point – FBE
Table	14.3.4.6.6	Coagulation Activation Data on Event Level: Frequencies and Percentages of Clinically Significant PT, PT (INR), aPTT, TAT, F1+2, D-dimer by Indication and Time Point – FBE
Table	14.3.4.6.7	Coagulation Activation Data on Event Level by Age Group: Frequencies and Percentages of Clinically Significant PT, PT (INR), aPTT, TAT, F1+2, D-dimer by Time Point – FBE
Table	14.3.4.6.8	Coagulation Activation Data on Event Level by Hospitalization: Frequencies and Percentages of Clinically Significant PT, PT (INR), aPTT, TAT, F1+2, D-dimer by Time Point – FBE
Listing	16.18.1	Markers of coagulation activation – SAF I
Listing	16.18.2	Markers of coagulation activation assess as clinically significant by the investigator – SAF I
Listing	16.18.3	Markers of coagulation activation – FBE
Listing	16.18.4	Markers of coagulation activation assess as clinically significant by the investigator – FBE

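### SAP 11.1 selects the inhibitor AESI by the whole SOC Investigations, so eight tables titled as inhibitor events would count other Investigations events too

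*SAP*

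**What the plan says.** SAP section 11.1 lists the AESI categories in item 10 (all treatment-emergent events) and repeats them in item 11 (related events). For inhibitors, both items give only "Fibrinogen inhibitory antibodies: SOC'Investigations". The thrombotic category shows the contrast: "Thrombogenicity: SMQ Embolic and thrombotic events (restricted to narrow search". Hypersensitivity and anaphylaxis are also selected by narrow SMQs, and transmission of infective agents by two named Preferred Terms.

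The same section states that adverse events are "presented by primary System Organ Class (SOC) and Preferred Term".

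SAP appendix 15.1 turns item 10 into Tables 14.3.2.14.1 to .4, the first titled "Treatment-Emergent Adverse Events with Fibrinogen Inhibitory Antibodies: Frequencies and Percentages of Patients by SOC and Preferred Term – SAF I and II". It turns item 11 into Tables 14.3.2.18.1 to .4, whose titles begin "Treatment-Emergent Related Adverse Events with Fibrinogen Inhibitory Antibodies".

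Separately, SAP section 11.6 reports the antibody assay itself. Results "will be categorized as positive, negative, or missing/not done", and they appear in Tables 14.3.4.5.1 to .3.

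**The concern.** A system organ class is the broadest level of the adverse event coding, and Investigations is not specific to antibodies. As a selection rule it picks up every event whose primary SOC is Investigations, whatever the test. The table titles then present that total as inhibitor events.

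The trial can produce such events. Protocol section 14.5.2 says: "Laboratory values which are outside the reference range and assessed as clinically relevant have to be controlled and documented as adverse events". That applies to values that first occur after BT524. Adults in Part I have coagulation markers at 10 post-dose time points (three on day 0, six follow-up days and the safety visit), together with repeated haematology and biochemistry. Part II repeats laboratory testing around each treated event.

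The label matters because development of fibrinogen antibodies is a listed safety criterion. Protocol section 14.5.1.4 also requires an inhibitor to be reported as a serious adverse event and the patient to be withdrawn. A total that mixes inhibitors with other test results could report inhibitor events where there were none, and would not match the assay-based tables in the same report.

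**Working it through.** No figure in the plan needs reproducing. The check compares the passages, counts the tables and gives an illustrative range.

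**1. Selection rules in SAP 11.1, items 10 and 11**

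| AESI category | Rule given |
|---|---|
| Hypersensitivity / anaphylaxis | Three SMQ searches, narrow |
| Thrombogenicity | One SMQ, narrow |
| Transmission of infective agents | Two named Preferred Terms |
| Fibrinogen inhibitory antibodies | SOC Investigations only |

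The SAP gives no inhibitor Preferred Term, no SMQ, and no link to a positive assay or to the mandatory SAE report.

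**2. What the rule selects**

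- Tables 14.3.2.14.1 to .4: every treatment-emergent event with primary SOC Investigations.
- Tables 14.3.2.18.1 to .4: every such event that is related. SAP section 5.3.2 imputes a missing causality as related for incidence summaries, so an event with no causality entry also counts here.
- Tables affected: 4 + 4 = 8.

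**3. Limits on what can enter**

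Not every abnormal laboratory value counts. Under protocol sections 14.5.2 and 14.6.2, only clinically relevant out-of-range values become adverse events, signs of an event already recorded are not separate events, and sites are told to prefer a clinical term to a laboratory term. The documents do not say which terms have Investigations as primary SOC. That an abnormal test result reported under a laboratory term would code there is an assumption.

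An inhibitor event would be missed only if it were coded to another SOC. The documents do not settle this either.

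**4. Illustrative size**

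Inputs: planned n = 23 (Part I) and n = 36 (Part II), from SAP section 3, Table 1. The number of patients k with an unrelated Investigations event, and the per-patient probability p of having one, are assumptions. True inhibitors are set to 0.

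Reported percentage = k / n; the correct value is 0%.

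| k | n = 23 | n = 36 |
|---|---|---|
| 1 | 1/23 = 4.3% | 1/36 = 2.8% |
| 2 | 2/23 = 8.7% | 2/36 = 5.6% |
| 3 | 3/23 = 13.0% | 3/36 = 8.3% |
| 5 | 5/23 = 21.7% | 5/36 = 13.9% |

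Probability that the total is not 0 = 1 − (1 − p)^n, taking patients as independent.

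| p | n = 23 | n = 36 |
|---|---|---|
| 0.02 | 37.2% | 51.7% |
| 0.05 | 69.3% | 84.2% |
| 0.10 | 91.1% | 97.7% |

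For the related-event tables the same formulas apply, with k and p restricted to related events, so the values would be no larger for the same patients. The tables that cover both parts would have a denominator of 23 + 10 + 3 = 36 planned patients if each patient is counted once.

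**The case against.** The strongest reply is that the line has a label and a SOC, and that the SOC may only say where the inhibitor term sits. The table titles fit that narrower reading, and the separate table shells, which are not available here, may carry the detail. But the SAP does not say this. On that reading the Preferred Term is missing and no usable rule remains, so the same edit is needed.

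Other points stand and limit the consequence:

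- The eight tables also show Preferred Terms, so a reader could see that an event is not an inhibitor. The rows do not correct the total or the title.
- True inhibitor status is reported from the assay in "Fibrinogen Inhibitory Antibodies Data: Frequencies and Percentages of Patients by Time Point" and in a corresponding event-level table. Inhibitor cases should also appear in the SAE and discontinuation outputs.
- Protocol section 14.6.1 names only thrombosis or TEE and suspected transmission of infective agents as AESIs. The inhibitor AESI tables are therefore an addition made in the SAP, and the protocol's own antibody criterion is served by SAP section 11.6.
- The overcount could be zero if no other event is coded to Investigations. The values of k and p have no source in the documents, and the preference for clinical terms pushes them down.

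These points argue against a serious rating. They do not make the rule correct, since it gives the right count only if no other Investigations event happens to occur.

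**Conclusion.** The concern holds. As written, the rule selects a whole SOC and the total would be reported under an inhibitor title in eight tables. This is an incorrect selection rule and not only a missing detail, and it should be fixed.

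The size cannot be computed from the documents. One unrelated patient is enough to turn a true 0% into 4.3% in Part I or 2.8% in Part II at the planned numbers. The wider ranges rest on the assumed k and p, on laboratory-term events coding to Investigations, and on no true inhibitor having occurred.

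Only descriptive safety tables are affected. No efficacy result and no primary PK result changes, and a true inhibitor would still be seen in the assay and SAE outputs.

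**What to change.** In SAP section 11.1, items 10 and 11, replace the SOC with a pre-specified list of Preferred Terms for fibrinogen inhibitor or anti-fibrinogen antibody development. Apply the list regardless of SOC, and agree it with drug safety before database lock. If the dictionary version in use has no suitable term, define the category by a positive inhibitory antibody result or by the SAE that the protocol requires.

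Use the definition for Tables 14.3.2.14.1 to .4 and 14.3.2.18.1 to .4, and cross-check the selected cases against the positive results in Tables 14.3.4.5.1 to .3.

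The cost is one line in each of two SAP items and a short term list. No new data or tables are needed.

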11.2 Deaths

Patient listings will be provided for patients with AEs leading to death.

11.3 Adverse events leading to discontinuation from study

Patient listings will be provided for patients with AEs leading to discontinuation.

11.4 Pregnancies

Pregnancy test results will be listed for all enrolled female patients (APE).

11.5 Vital signs

Vital signs are measured with the following method/unit:

- Blood pressure [mmHg]
- Heart rate in beats/min measured by pulse rate
- Body temperature in grade Celsius [°C] (tympanic measurements)

Measured values of vital signs will be summarized descriptively across the measurement time points (per observation period, cf. study protocol flowchart section 3) for part I (SAF) and on event level from part II (separated by ODP/ODT, hospitalization, age group) for FBE. Note that 'baseline' refers to the pre-dose measurement within each observation period of the indication/event. A listing with all patients vital signs data will be presented.

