4.1.2.2 Study populations (part II – event based)

For part II (ODP/ODT), the following specifications as to analysis sets apply:

With respect to the evaluation of efficacy, surrogate efficacy and safety of the single or repetitive intravenous infusions of BT524, each bleeding event will be considered as an individual case in the primary analysis.

There are 2 event-based analysis sets:

Full Bleeding Event Set (FBE)

All events treated with any portion BT524, and with at least one efficacy assessment.

Per Protocol Bleeding Event Set (PPBE)

Subset of FBE of patients who are compliant with the study protocol (i.e. without any major protocol deviations in part II) and includes all bleeding events without any major protocol deviation with potential to impact the results of the efficacy analysis.

In the BDRM, dated 25-Jun-2020, all minor and major protocol deviations on bleeding event level were reviewed and agreed upon. Following from the decisions taken, assignments to PPBE analysis population were done. A complete list of all protocol deviations is attached to the BDRM minutes and included in the listings of the final analysis.

As agreed in the BDRM (25-Jun-2020), all bleeding events documented for a patient with at least one major protocol deviation (i.e. patients excluded from PP II set) will be excluded from the PPBE.

In addition, selected efficacy analyses for bleeding events and surgical interventions will be analyzed per patient in the FBE and PPBE populations as defined above.

With respect to the evaluation of adverse events, the patient is the relevant unit for analyzing these endpoints. Therefore, their evaluation across all parts is based on the safety population as defined in section 4.1 above.

5 General Statistical Methods and Definitions

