- Units of transfusion products infused, e.g., allogenic or autologous blood (packed red blood cells, fresh whole blood), platelets, given to counteract hemodynamic instability at the day of BT524 administration or 1 day after.

- Consumption of BT524 (dose per kilogram body weight, dose per infusion and total dose) required pre-, intra- or post-operatively for effective treatment of surgical bleeding events.
- Quality of wound healing assessed after wound healing is expected to be completed.

Furthermore, MCF as a surrogate efficacy parameter will be evaluated pre-dose and at 1 hour post-end of each IV infusion (including repetitive infusion for one bleeding event) by means of non-confirmatory t-test(s) pre/post comparison plus correlation between MCF and fibrinogen activity. Also MCF will be presented as a whisker box plot and also listed.

Descriptive summary statistics including changes from baseline for the fibrinogen activity will be provided for each age group. MCF and fibrinogen activity values from additional samplings (beside pre-dose and 1 hour post-dose) taken as required per investigator will be listed and not used in the analyses described above. These analyses will be conducted on event level, i.e. based on the event based FBE and PPBE analysis set. Otherwise, details correspond to those of part I analysis, except that the testing is considered as non- confirmatory.

With respect to the two evaluation concepts of efficacy, the concept when multiple events per patient are to be handled as individual cases is considered primary analysis within the framework of secondary analyses of part II.

Descriptive summary statistics and a listing for the fibrinogen antigen at screening will be provided for each age group on patient level (SAF, FAS, and PP analysis sets).

11 Safety

All assessments will be done for part I and part II separately.

APE-Set will be used to present overall numbers of AEs incl. NTEAEs. All safety analyses will be based on the SAF.

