11.8 Clinical safety laboratory

All safety lab values will be re-calculated to SI units before further processing.

The following statistical analyses will be presented for part I (SAF) and on event level from part II for FBE (separated by ODP/ODT, hospitalization, age group as appropriate) per lab test (as listed subsequently). Note that 'baseline' refers to the pre-dose measurement within each observation period of the indication/event:

1. Quantitative data will be examined for trends using descriptive statistics (number of patients/events with data, number of patients/events with missing values, mean, SD, median, minimum, and maximum) of measured values at baseline and each planned post-baseline visit over time.
2. Qualitative data based on laboratory specific normal ranges will be categorized according to the categories (e.g. below normal/normal/above normal) and presented as number and relative frequency of patients (and/or events).
3. Number and percentages of patients/events with on treatment values considered as clinically significant (CS) by the investigator will be tabulated (across planned visits). Out of range values not assessed for clinical significance are not included in the analysis and are provided in Listing.

Note that in the listings, laboratory values that are outside the normal range will additionally be flagged. Any out-of-range values that are identified by the investigator as being clinically significant will also be shown in an extra data listing. Additionally, a separate listing showing the normal ranges will be generated.

Hematology and clinical chemistry

Hematology tests include RBC, WBC, platelet count, hemoglobin, and hematocrit (all quantitatively).

Biochemistry tests measure aspartate aminotransferase, alanine aminotransferase, γ -glutamyltransferase, alkaline phosphatase, total bilirubin, creatinine, urea, potassium, sodium, calcium, chloride (all quantitatively).

Urinalysis

Blood, leukocytes, protein, glucose, ketones, nitrite, bilirubin, urobilinogen were measured only qualitative, pH was measured quantitative. For the analysis only qualitative results will be used (for pH the normal ranges are used for classification of results into "normal", "abnormal"). Frequencies and percentages of normal and abnormal values will be presented. The quantitative results will only included in the listings.

Markers of coagulation activation

Coagulation activation parameters include PT, PT(INR), aPTT, TAT, F1+2, D-dimer.

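### Part II event-level vital sign and laboratory safety outputs use FBE, a set that requires an efficacy assessment, and have no exposure-only counterpart

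*SAP*

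**What the plan says.** **The sets.** SAP 4.1.2.2 states: "There are 2 event-based analysis sets". The wider one, FBE, is defined as: "All events treated with any portion BT524, and with at least one efficacy assessment". The other, PPBE, is a subset of it. At patient level, SAP 4.1.2.1 defines SAF II by exposure to BT524 in Part II, with no efficacy condition.

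**The general rule.** SAP 11 says: "All safety analyses will be based on the SAF". Protocol 15.2.6 likewise bases the safety analysis on the safety population.

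**The specific instructions.**
- SAP 11.5 presents Part II vital signs "on event level from part II (separated by ODP/ODT, hospitalization, age group) for FBE".
- SAP 11.8 presents the safety laboratory "on event level from part II for FBE (separated by ODP/ODT, hospitalization, age group as appropriate) per lab test". Coagulation markers belong to the same section, and the output list in SAP 15.1 confirms their set, for example: "Coagulation Activation Data on Event Level: Descriptive Statistics of PT, PT (INR), aPTT, TAT, F1+2, D-dimer by Indication and Time Point – FBE".
- SAP 11.6 summarises inhibitory antibodies by patient on the SAF in both parts, and adds a summary "on event level from part II for FBE".
- SAP 11.10 (physical examination) names no set. SAP 15.1 puts the patient-level Part II table on SAF II and the event-level shift table on FBE.

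**The concern.** A set used to describe safety should depend on exposure and nothing else. The SAP keeps to this at patient level, where SAF II and FAS II are separate sets. At event level it then uses an efficacy set for safety data, against its own general rule. SAP 2.1 declares the analysis consistent with protocol version 6.0 and lists the exceptions, and this is not one of them.

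If the SAP is followed as written, an event in which BT524 was infused but no efficacy assessment was recorded drops out of the Part II vital sign, laboratory and coagulation results. What is at stake is the completeness of the event-level safety data, and whether a reader could tell that they are incomplete.

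**Working it through.** No arithmetic settles this point. The check is to trace the sets through the planned outputs.

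**Step 1. Sets by level (SAP 4.1.2.1 and 4.1.2.2).**

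| Level | Exposure only | Exposure plus efficacy assessment | Without major deviation |
|---|---|---|---|
| Patient | ITT II, SAF II | FAS II | PP II |
| Event | none | FBE | PPBE |

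The event-level counterpart of the SAF is missing.

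**Step 2. Part II outputs in SAP 15.1.**

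| Data | Event-level tables, all FBE | Part II listings, all FBE | Part II SAF table |
|---|---|---|---|
| Vital signs | 14.3.4.2.1 to .3 (3) | 16.13.2 | none |
| Haematology | 14.3.3.1.3 to .8 (6) | 16.10.3, 16.10.4 | none |
| Chemistry | 14.3.3.2.3 to .8 (6) | 16.11.3, 16.11.4 | none |
| Urinalysis | 14.3.3.3.3 to .8 (6) | 16.12.3, 16.12.4 | none |
| Coagulation markers | 14.3.4.6.3 to .8 (6) | 16.18.3, 16.18.4 | none |
| Inhibitory antibodies | 14.3.4.5.3 | 16.17.2 | 14.3.4.5.2 |
| Physical examination | 14.3.4.4.4 | 16.16.3, 16.16.4 | 14.3.4.4.2 |
| Ultrasonography | no table | 16.15.2 | none |

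The first five rows give 3 + 6 + 6 + 6 + 6 = 27 tables on FBE with no SAF II alternative.

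**Step 3. Do the listings recover the data?** SAP 5.1 promises that all collected data will be listed, and 11.5 promises a vital signs listing for all patients. The FBE labels in step 2 contradict both.

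**Step 4. Would the loss be visible?** Event accounting (14.1.1.1.7 to .10), event-level deviations (14.1.1.3.3, Listing 16.3.3) and Part II dosing, infusion rate and interruption outputs are all on FBE or PPBE. None counts treated events outside FBE. Listing 16.2.7 (patient visits, APE II) might reveal such an event to someone comparing records by hand, but the SAP does not specify its content.

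**Step 5. How many events?** Events lost = treated Part II events − FBE events, which is zero or more. The documents give neither term. The result turns on what counts as an efficacy assessment, which the SAP leaves undefined:
- Protocol flowcharts 3.1 to 3.5 schedule MCF and fibrinogen activity before the dose for every Part II event. If a pre-dose MCF counts, few events or none fall out.
- Protocol 14.4.2 lists BT524 consumption among the efficacy parameters. If that counts, every infused event qualifies.
- If only post-dose information counts, an event needs the 1-hour MCF or the investigator's rating, which protocol 14.4.5.2.1 places at hospital discharge or at the end of the treated event. An event cut short could then lack both.

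**The case against.** The strongest reply is that the effect is small and the main safety evidence lies elsewhere.

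- Adverse events, serious events, deaths, discontinuations, infusion-related reactions and events of special interest are analysed by patient on the SAF, and adverse events are listed on the APE. Protocol 14.5.2 requires laboratory values that are out of range, clinically relevant and new after BT524 to be recorded as adverse events. This stands in full.
- The entry condition for FBE is easily met, given pre-dose sampling and a response rating for every event. This is likely, but it depends on an undefined term.
- An event cut short would often lack later vital signs and laboratory values anyway, and the tables concerned are descriptive. This is fair. It bears on size, not on whether the rule is broken.
- SAP 4.1.2.2 calls for event-based evaluation of safety, so 11.5 and 11.8 needed an event set, and FBE was the wider of the two available. This explains the choice as an omission. It does not reconcile it with SAP 11.

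A reader might infer more than the documents support:
- **That antibody results are lost from every summary.** They are not. The FBE table is additional to the patient-level SAF II table.
- **That the excluded events would mostly be stopped infusions, early reactions, transfers or deaths, so that safety looks better than it is.** No passage shows this. A stopped infusion does not erase a pre-dose sample or prevent a response rating.

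**Conclusion.** The inconsistency is real. Part II vital signs, haematology, chemistry, urinalysis and coagulation markers are tabulated and listed only on a set that requires an efficacy assessment, against SAP 11 and protocol 15.2.6. The event-level antibody table, the physical examination shift table and the Part II antibody, physical examination and ultrasonography listings share the problem. For antibodies and physical examination it is limited to event-level outputs, because the SAF II tables remain. Adverse event analyses are untouched.

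The number of events affected is unknown and may be zero, and nothing can be said about the direction or size of any bias. The conclusion assumes only that the SAP and its output list are applied as labelled. It is worth correcting because the SAP breaks its own stated rule, any loss would go uncounted, and the repair is nearly free.

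**What to change.** 1. Add to SAP 4.1.2.2 an event-level safety set: all Part II events treated with any portion of BT524.
2. Use it for the event-level tables and listings of 11.5, 11.6 and 11.8, for the 11.10 shift table (14.3.4.4.4) and physical examination listings, and for ultrasonography Listing 16.15.2. Relabel SAP 15.1 to match.
3. Report the number of treated Part II events outside FBE, including when it is zero.
4. Keep FBE and PPBE for efficacy.

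The cost is one set definition and relabelled outputs, with no new data. If every treated event proves to be in FBE, the results do not change and the reported count shows it.
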